The clinical partners have developed a protocol for verification of system performance in clinical care of newborn infants. Three groups of infants will be studied. Twenty term newborn infants immediately after delivery by caesarian section and again on the following day when stable, twenty preterm infants when their respirator is adjusted to normalise blood pCO2, and twenty unstable newborn infants during a 24 hours period. The purposes are to verify that the instrument produces expected changes in brain oxygenation and blood flow after birth, and when blood pCO2 changes, and that the variability of readings when changing sensor position and the signal loss due to movement and other disturbances during clinical care is of acceptable magnitude. Finally, users will report on user-friendliness as well as usefulness and trustworthiness of the data.

D5.1 Definition of the Clinical Protocol

Classification PU

2. Introduction

This document includes the draft clinical protocol.

D5.1 Definition of the Clinical Protocol

Project - No 620996

Date 31.03.14

Classification PU

3. Clinical protocol

3.2. Background

Over the last two decades, the percentage of preterm births in the Western hemisphere rose by ~20%. Preterm birth is associated with an increased risk of brain damage and neurodevelopmental deficit. Brain injury in preterm babies is a complex mixture of destructive events and developmental disturbances affecting the developing brain. The concept of gestationally determined regional vulnerability in the brain has been emphasized: the site and nature of the injury sustained being determined by a combination of the characteristics of the insult, the specific tissue and cell vulnerability and the gestation of the infant. The vulnerability of the white matter in the brain of premature babies is important. However, a more complex pan-brain developmental growth disruption is associated with preterm birth.

Different pathophysiological mechanisms are involved in injuring the developing brain, in particular infection-inflammation, pre- and/or postnatal malnutrition, and abnormalities in systemic and cerebral haemodynamics and oxygen supply.

The most vulnerable period regarding the latter is represented by the first hours and days after birth due to abnormal haemodynamic adaptation during the transitional circulation combined with the impact of respiratory distress syndrome. This leads to hypoperfusion, hypoxia/hyperoxia, ischemia and other issues. Disturbance of cerebral blood flow, i.e., hypoperfusion, is related to impaired cerebral autoregulation. Autoregulation is the ability to keep the organ blood flow constant despite fluctuations in perfusion pressure and it is accomplished by regulation of the arterial tone so that low perfusion pressure results in vasodilation and high pressure results in vasoconstriction. Cerebral autoregulation has limited capacity in critically ill premature babies and is thought to be particularly fragile in the immature brain. Impaired cerebral autoregulation leads to pressure passive flow which is a state where the blood flow follows the blood pressure: large fluctuations in flow seem to be involved in cerebral haemorrhages in premature infants due to rupture of the immature blood vessels. As tissue hypoxia as well as tissue hyperoxia cause brain injury, both should be avoided.

To that end, a continuous and non-invasive monitoring of cerebral perfusion and/or oxygenation has been searched for an end-organ monitoring with sufficient high time resolution to guide evidence-based treatment interventions is lacking. [Greisen G, 2011] Near infrared spectroscopy has the potential to become that monitor of the brain.

Near-infrared spectroscopy (NIRS) is a non-invasive technology that has been utilised to assess the adequacy of peripheral and cerebral oxygenation in the preterm infant. [Menke J, 2003] Near-infrared light penetrates deep into the tissue, and through spectroscopy, it is possible to monitor tissue oxygenation. NIRS uses the relative transparency of human tissue to light in the near-infrared region of the spectrum. The oxygen-dependent absorption of light by haemoglobin enables the calculation of relative changes in the oxygenated and deoxygenated haemoglobin. [Wolf M, 2009] The NIRS has been used in newborns since 1985 and it is particularly suitable for the neonatal population due to their thin scalp and skull. [Brazy JE, 1985] Quantification of oxygenation in a percentage from 0 to 100% has

D5.1 Definition of the Clinical Protocol

Classification PU

been possible for 10 years and near-infrared spectroscopy commercial devices are currently being used in clinical trials as cerebral oximeter. [Hyttel-Sørensen S, 2013] This is most often done by spatially resolved spectroscopy. The assumption behind is that light propagates in a diffusional manner in a highly scattering media such as human tissue, and that the light attenuation by scattering is constant with light distances over 3 centimetres.

However, the usefulness of this approach depends on the assumption of stable oxygen consumption which depends both on the local tissue demand, perfusion (delivery) and oxygenation (supply). In order to estimate the oxygen consumption and the cerebral oxygen metabolism, a non-invasive, continuous, cot-side monitor of brain perfusion and oxygenation is needed and remains an unfilled niche in clinical care.

The BabyLux project aims to provide a precise, accurate, and robust device to continuously monitor cerebral oxygen metabolism and blood flow in critically ill newborn infants. This will be achieved by combining time resolved near-infrared spectroscopy (TRS) with newly developed diffuse correlation spectroscopy (DCS) in a single device. The innovative aspects of the project are related to the use of advanced solutions, based on state-of-the-art photonic components, which have already been tested in laboratory and clinical tests on adults.

3.2.1 Time Resolved Near-infrared spectroscopy (TRS) and Diffuse Correlation

Spectroscopy (DCS)

The proposed solution will integrate two advanced photonic techniques, TRS and DCS. Both techniques rely on the use of an optical fibre probe (sensor) to illuminate with very low power near infrared light the scalp and to collect the diffusively reemitted optical signal that has propagated through the scalp and skull and therefore carries information on the deeper cortical region. The different absorption spectra of oxygenated and deoxygenated haemoglobin in the near infrared range allows for the noninvasive monitoring of the two species in the cortical tissue.

TRS and DCS prototypes are available and have been technically tested in laboratory settings and successfully validated during preclinical trial on adult volunteers and patients. [Torricelli A, 2011, Durduran T, 2010]

3.2.2 Measured TRS/DCS parameters

TRS measures the attenuation and the temporal broadening of relatively short light pulses (pulse duration ~100 ps) through a diffusive medium (e.g. a neonate's head). TRS has the ability to resolve path-lengths (or equivalently time-of-flights) of photons that have propagated through the tissues. This enables TRS to separate the absorption and scattering coefficients allowing for absolute measurements, and to utilize time-gating of path-lengths to emphasize signals from deeper tissues. This is particularly important for separating intra-and extra-cerebral signals for brain monitoring. [Torricelli A, 2014]

DCS relies on the fact that temporal correlation of light fields in turbid media also obeys a diffusion equation, albeit a slightly different one than is used for TRS. Thus DCS shares the light penetration advantages of TRS, but, since DCS explicitly measures red blood cell movement, it provides a direct measure of quantities such as cerebral blood flow (CBF). [Durduran T, 2010]

The specific combination of DCS and TRS allows for the assessment of cerebral oxygen metabolism and CBF in a complete (i.e. CBF and oxygenation are simultaneously and independently provided), accurate (i.e. based on absolute measurements of optical parameters) and robust (i.e. potentially less affected by artefacts related to superficial systemic activity or sensor/head movements) way.

Date 31.03.14

Classification PU

D5.1 Definition of the Clinical Protocol

3.3. Aim

Aim of this project is to perform clinical measurements using the BabyLux instrument in different clinical real-life settings to validate this new technology in terms of feasibility, reproducibility, and user friendliness in neonatal medicine, in order to provide a precise, accurate robust device to continuously monitor cerebral oxygen metabolism and blood flow in newborn infants.

3.4. Methods

The BabyLux integrated system will be validated in real-life settings by monitoring cerebral oxygenation and haemodynamics in healthy term neonates and critically ill preterm and term infants. Target tests, aimed to measuring main features related to both technical and physiological parameters, will be used.

Parental written informed consent will be asked.

The BabyLux system is tested in four different real-life settings to measure:

- (3.4.1) the rise in oxygenation and change in blood flow during the minutes after birth to specify the expected range of measurement;
- (3.4.2) the precision and reproducibility of measurements by reapplying the optodes several times on slightly different sites of the head in a relatively steady condition;
- (3.4.3) the cerebral vaso-reactivity to arterial carbon dioxide tension in mechanically ventilated newborns to monitor induced changes in cerebral blood flow;
- (3.4.4) the user friendliness and loss of signal in routine care situations (e.g. during 24hour monitoring of neonates undergoing intensive care).

Infants with genetically defined syndromes or congenital malformations are excluded from the study.

3.4.1 Changes in cerebral oxygenation and haemodynamics after birth

Inclusion criteria:

- term newborns (with a gestational age > 37 weeks)
- delivered by an uncomplicated elective caesarean section

Exclusion criteria:

- Apgar score < 8
- need for respiratory support or supplementary oxygen during the transition

Immediately after birth the infants is wrapped in warm towels and the head and right hand are cleaned with towels to reduce vernix and amniotic fluid, which can influence sensor signal quality. The timer is started at the point of umbilical cord clamping. As soon as possible, after drying the head, the TRS/DCS sensor is positioned in the fronto-parietal region of the newborn's head and held in position by hand for 10 minutes from cord clamping. The pulse oximeter, to measure arterial oxygen saturation (SaO2) is positioned on the right arm or wrist (at the pre-ductal level), as soon as possible.

SaO2 and pulse are measured continuously with two Masimo SET pulse oximeter (Masimo Coorporation, CA, USA).

3.4.2 Precision and reproducibility of measurements

The reproducibility of measurements are evaluated by reapplying the BabyLux sensor several times on slightly different sites of the head in a relatively steady condition. Repeated measurements are carried out on the same infants enrolled in the 4.1 study, more than 24 hours after delivery.

D5.1 Definition of the Clinical Protocol

Date 31.03.14

Classification PU

The BabyLux sensor is positioned on the fronto-parietal region and then removed and replaced: six measurements of 30 seconds each with total sensor lift-off of 30 seconds between measurements are carried out.

3.4.3 The cerebral vaso-reactivity to arterial carbon dioxide

The cerebrovascular reactivity to changes in arterial carbon dioxide tension is tested in mechanically ventilated newborns.

Inclusion criteria:

- gestational age <37 weeks
- postnatal age at least 24 hours
- mechanically ventilation
- clinical stability
- normal brain ultrasound
- transcutaneous pCO2 monitoring (tcpCO2)

In case of hypercapnia (tcpCO2>7 kPa) or hypocania (tcpCO2<5 kPa) clinical changes in ventilatory settings are introduced according to routine clinical care in order to normalise pCO2. At least 20 min is allowed to assess the full effect of the change in ventilator setting. This may be repeated if necessary to normalise the tcpCO2.

3.4.4 Assessment of the user friendliness and loss of signal in routine care

The user friendliness and loss of signal are evaluated in routine care situations during 24hour monitoring of neonates undergoing intensive care.

Inclusion criteria:

- postnatal age < 28 days
- clinical unstability
- ventilatory support by mechanical ventilation or nasalCPAP
- transcutaneous pCO2 monitoring

The BabyLux sensor is positioned on the fronto-parietal region and replaced every 4 to 6 hours to check for skin integrity.

The BabyLux system will be equipped with dedicated software developed by the BabyLux partners (Hemophotonics SL, Politecnico di Milano) to provide in real time the time course of the measured parameters: oxygen tissue saturation (StO2) and cerebral blood flow index (CBFi). Other data to indicate signal quality and information to assist the user manually to improve the signal if necessary is also available. The clinicians will be made aware that the data is experimental, but are free to consider them in clinical decisions if they choose to do so.

All operations of the system will be logged, as well as all manipulation of the sensor.

The user friendliness will be assessed by all users - physicians and nurses. On basis on their experience with the actual infant in the time period they have been involved, they will report on Likert scales from 'very bad' to 'very good' on the parameters 'operating the system', 'presentation of data', 'trustworthyness of StO2', 'trustworthyness of CBFi'

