3.6.2 Data analysis

- (4.1) The SpO2, StO2, oxygen extraction (OE: SpO2-StO2), fractional oxygen extraction (FTOE: SpO2-StO2)/SpO2), CBFi, and cerebral metabolic rate of oxygen index (CMRO2i: OE x CBFi) will be graphed versus time after cord clamping. It is expected that StO2 will rise by about 30%, and that CMRO2i and FTOE will remain relatively constant. The results will be compared to the literature.
- (3.4.2) Reproducibility (test-retest variability) will be determined by ANOVA.
- (3.4.3) Data containing 0.5 kPa change in tcpCO2 or more within 15 minutes after a change in ventilator settings will be analyses for CBFi-tcpCO2 reactivity. One minute of data just before the change and one minute of data 15 minutes later will be used. The expected reactivity is 30%/kPa.
- (3.4.4) Signal loss will be calculated per 24 hours. This will be compared to the results of the SafeBoosC-II. The system operations and sensor manipulations will be classified into suitable groups and tabulated. The mean Likerts scores will be calculated and the free text comments classified and typical comments used *verbatim* in the reporting process.

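### The summary says users will report on the usefulness of the data, but none of the four Likert items in 3.4.4 asks about it, so usefulness could surface only incidentally in free text

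*Protocol*

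**What the plan says.** Four places in the protocol bear on this.

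- **Opening summary.** After the sentence listing the purposes of the study, it adds: "Finally, users will report on user-friendliness as well as usefulness and trustworthiness of the data". That names three things users will report on.
- **Section 3.3 (Aim).** The aim is to "validate this new technology in terms of feasibility, reproducibility, and user friendliness in neonatal medicine". Usefulness is not named.
- **Section 3.4.4.** It states that "The user friendliness will be assessed by all users - physicians and nurses". Each user rates, from experience with the particular infant, on scales running from very bad to very good, "on the parameters 'operating the system', 'presentation of data', 'trustworthyness of StO2', 'trustworthyness of CBFi". The section also says that clinicians may see the readings and "are free to consider them in clinical decisions if they choose to do so". What is logged is system operation and sensor handling.
- **Section 3.6.2.** For this part of the study, "The mean Likerts scores will be calculated and the free text comments classified and typical comments used" word for word in the report.

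**The concern.** The summary treats usefulness and trustworthiness as separate things, and they are. A nurse or physician may believe a reading and still find that it adds nothing at the cot-side. Ratings of trust therefore cannot stand in for ratings of usefulness.

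Section 3.4.4 fixes the rated items by name, and usefulness is not among them. This is a matter of what is collected, not of how it is analysed, so a statistical analysis plan could not repair it: it cannot summarise answers to a question that was not put. At stake is whether the report can deliver one of the three user assessments announced in the summary for the 20 infants in the intensive-care group.

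**Working it through.** No arithmetic beyond counting applies. The check sets what is announced against what is collected, and then looks for any other source.

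**Step 1. Items for each announced topic.** The topics come from the summary and the items from 3.4.4.

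| Topic in the summary | Likert items in 3.4.4 | Count |
|---|---|---|
| User-friendliness | operating the system; presentation of data | 2 |
| Trustworthiness | StO2; CBFi | 2 |
| Usefulness | none | 0 |

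The counts add up to 2 + 2 + 0 = 4, which is the full list.

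**Step 2. Could an existing item be read as covering usefulness?** The two trust items ask whether a reading is believed. The item on presentation asks how the data are shown. The item on operation asks about handling the device. None asks whether the reading helped.

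**Step 3. Does the log cover it?** Section 3.4.4 logs system operations and sensor manipulations. Clinicians may take the readings into account, but the section specifies no record of whether they did or of whether they judged them helpful.

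**Step 4. Does the free text cover it?** Section 3.6.2 refers to "the free text comments classified and typical comments used" in reporting, which presupposes that comments are collected. Section 3.4.4 mentions neither a comment field nor a prompt. If comments are collected, some users may write about usefulness. Such remarks show that a view exists among those who wrote. They give no score, and a user's silence cannot be read as either approval or disapproval.

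**Result.** Usefulness has 0 of 4 rated items and one possible incidental source, the free text.

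**The case against.** The strongest reply is that this is a one-word mismatch in a document that calls itself a draft. Usefulness as something users report appears once, in the summary. The aim in 3.3, the list of settings in 3.4 and the heading of 3.4.4 speak of user friendliness and, in the last two, loss of signal. No sample size, hypothesis or performance result rests on usefulness. Section 4 says the protocol will be reworked into a clinical investigation plan, where such a point can be tidied. All of this is fair and it limits the severity. It does not remove the mismatch, because the summary makes an explicit statement about what users will report and the item list does not follow it through.

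A reader might infer more than the protocol supports, in four ways.

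- *That a stated purpose of the study goes unanswered.* The purposes are listed in their own sentence of the summary. The user reports follow in a separate one, and 3.3 does not name usefulness.
- *That there will be no usefulness data at all.* The comments that 3.6.2 plans to classify could carry remarks on it.
- *That the information would be lost for good.* The listed items are tied to experience with the particular infant, but nothing says usefulness must be rated that way, and nothing prevents asking the physicians and nurses afterwards. Later recall would be weaker evidence, but it would still be evidence.
- *That the free-text analysis has no source.* Section 3.6.2 presupposes a comment field. Its absence from 3.4.4 is a missing detail, not a contradiction.

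One caveat remains: the item list in 3.4.4 ends without a full stop in the text as read, so a cut in text extraction cannot be wholly excluded. Nothing shows that an item was lost.

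**Conclusion.** The point holds in a limited form. The summary says users will report on usefulness, yet none of the four items fixed in 3.4.4 asks about it. Usefulness could emerge only incidentally from comments, and could not be reported as a score or for all users.

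The severity is low to moderate. The outcome is descriptive, and the measurements of oxygenation, blood flow, reproducibility, CO2 reactivity and signal loss are untouched. The conclusion assumes that the list in 3.4.4 is complete as printed and that the form carries no usefulness prompt that the protocol leaves unmentioned. If either assumption fails, the remaining task is to bring the text of 3.4.4 into line with the form.

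**What to change.** In 3.4.4, add two Likert items, 'usefulness of StO2' and 'usefulness of CBFi', alongside the two trust items, which are already split in the same way. State in the same section that the form has a free-text field, so that the comment analysis in 3.6.2 has a named source. The new items can be summarised with the others as mean scores, so 3.6.2 needs no new method.

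If usefulness is not meant to be assessed, delete the word from the summary. That would also bring the summary closer to the aim in 3.3.

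A yes/no question on whether a reading was considered in a clinical decision is not needed for this fix. Considering a reading does not show that it was useful, and clinicians are told the data are experimental, so a 'no' would be hard to interpret.

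The form grows from four rated items to 4 + 2 = 6 per user. The change can be made when the draft is turned into the clinical investigation plan.

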3.5. Data recording and management

Subjects are sequentially numbered. The list of subjects with their basic clinical data will be recorded in an electronic file.

During all measurements, NIRS data will be stored timelocked with other monitored

variables as relevant (arterial oxygen saturation, transcutaneous pCO2, mean arterial blood pressure, pulse rate).

Before analysis all data will be graphed and screening for artefacts by visual inspection. After removal of artefacts, the data will be locked.

3.6. Data analysis and statistical analysis

3.6.1 Sample size

60 neonates will be studied at the two sites.

- 20 for (4.1) and (4.2)
- 20 for (4.3)
- 20 for (4.4)

We will aim at the inclusion of approximately equal number of infants at each site for each of the groups.

3.6.2 Data analysis

- (4.1) The SpO2, StO2, oxygen extraction (OE: SpO2-StO2), fractional oxygen extraction (FTOE: SpO2-StO2)/SpO2), CBFi, and cerebral metabolic rate of oxygen index (CMRO2i: OE x CBFi) will be graphed versus time after cord clamping. It is expected that StO2 will rise by about 30%, and that CMRO2i and FTOE will remain relatively constant. The results will be compared to the literature.
- (3.4.2) Reproducibility (test-retest variability) will be determined by ANOVA.
- (3.4.3) Data containing 0.5 kPa change in tcpCO2 or more within 15 minutes after a change in ventilator settings will be analyses for CBFi-tcpCO2 reactivity. One minute of data just before the change and one minute of data 15 minutes later will be used. The expected reactivity is 30%/kPa.
- (3.4.4) Signal loss will be calculated per 24 hours. This will be compared to the results of the SafeBoosC-II. The system operations and sensor manipulations will be classified into suitable groups and tabulated. The mean Likerts scores will be calculated and the free text comments classified and typical comments used *verbatim* in the reporting process.

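### The CO2-reactivity read-out and its 0.5 kPa selection rule stop at 15 minutes, short of the 20 minutes or more that the method section gives for the full effect, and no reason is stated

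*Protocol*

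**What the plan says.** Two sections of the protocol describe the same experiment in ventilated preterm infants.

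- **Section 3.4.3 (method).** After routine-care changes to the ventilator, "At least 20 min is allowed to assess the full effect of the change in ventilator setting". The next sentence adds: "This may be repeated if necessary to normalise the tcpCO2".
- **Section 3.6.2 (analysis).** Episodes qualify by this rule: "Data containing 0.5 kPa change in tcpCO2 or more within 15 minutes after a change in ventilator settings". The read-out is then fixed: "One minute of data just before the change and one minute of data 15 minutes later will be used". The benchmark follows: "The expected reactivity is 30%/kPa".

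No section gives a reason for stopping at 15 minutes or says that the response is complete by then. Section 3.5 has the NIRS data stored time-locked with transcutaneous pCO2 during all measurements, so later data from the same episode will exist.

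**The concern.** The read-out comes 5 minutes before the shortest period that the method section itself sets aside for the full effect. A SAP could not simply supply this as a missing detail, because the protocol fixes the window and fixes it at odds with its own method section.

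The stake is the check on the blood-flow channel. The figure of 30%/kPa is the only number in section 3.6.2 against which CBFi is set. The other expectations concern StO2, which is oxygenation, or say that CMRO2i and FTOE stay roughly constant, with no figure. The protocol's opening summary names the response to a change in blood pCO2 as one of the things the study is meant to verify. Only 20 infants are planned for this part, and usable episodes depend on ventilator changes that arise in routine care. Each lost or noisy episode therefore counts.

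**Working it through.** **Inputs from the protocol**

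- Time given for the full effect: at least 20 min (3.4.3).
- Read-out: 15 min after the change (3.6.2).
- Selection: tcpCO2 change of 0.5 kPa or more within 15 min (3.6.2).
- Expected reactivity: 30%/kPa (3.6.2).
- Infants in this part: 20 (3.6.1).

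The protocol derives no figure here that could be reproduced; 30%/kPa is stated as an expectation.

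**Step 1. The gap.** 20 − 15 = 5 min, and 5/20 = 25% of the stated minimum.

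**Step 2. The signal at the threshold.** 0.5 kPa × 30%/kPa = a 15% change in CBFi.

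**Step 3. How much of the change is present at 15 min.** The protocol gives no time course, so this step rests on assumptions. Take a first-order response f(t) = 1 − exp(−t/τ), with τ = −20/ln(1 − F), where F is the fraction complete at 20 min. As a slower alternative, take a straight ramp ending at 20 min. The last two columns are 0.5 ÷ ratio and 1 ÷ ratio.

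| Assumed shape | τ (min) | f(15) | f(15)/f(20) | 20-min change needed to show 0.5 kPa at 15 min | Error in the ratio relative to 20 min |
|---|---|---|---|---|---|
| First-order, F = 0.90 | 8.69 | 0.822 | 0.914 | 0.55 kPa | 1.09 |
| First-order, F = 0.95 | 6.68 | 0.894 | 0.941 | 0.53 kPa | 1.06 |
| First-order, F = 0.99 | 4.34 | 0.968 | 0.978 | 0.51 kPa | 1.02 |
| Straight ramp | – | 0.75 | 0.75 | 0.67 kPa | 1.33 |

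The last column assumes the same absolute measurement noise at both times. A given error in the CBFi change is then divided by a smaller tcpCO2 change at 15 min.

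**Step 4. Is the ratio biased?** Reactivity is the percentage change in CBFi divided by the change in tcpCO2, both read at the same time t. If both follow the same f(t), it cancels, and the result is 30%/kPa at 15 and at 20 min alike.

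If one signal trails the other by L minutes, it does not cancel:

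- tcpCO2 lags: R(t) = 30 × f(t)/f(t − L)
- CBFi lags: R(t) = 30 × f(t − L)/f(t)

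Example with F = 0.95, L = 2 and tcpCO2 lagging. At 15 min, 30 × 0.894/0.857 = 31.3. At 20 min, 30 × 0.950/0.933 ≈ 30.6.

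| Assumed shape and delay | tcpCO2 lags: 15 min / 20 min | CBFi lags: 15 min / 20 min |
|---|---|---|
| F = 0.95, L = 1 | 30.6 / 30.3 | 29.4 / 29.7 |
| F = 0.95, L = 2 | 31.3 / 30.6 | 28.8 / 29.5 |
| F = 0.90, L = 3 | 32.9 / 31.4 | 27.3 / 28.6 |
| Ramp, L = 3 | 37.5 / 35.3 | 24.0 / 25.5 |

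In every row the departure from 30%/kPa is larger at 15 min than at 20 min, and its sign depends on which signal trails. Over the first-order rows, the part removed by moving to 20 min is about 0.3 to 1.5%/kPa.

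**The case against.** The strongest defence is that section 3.4.3 can be read as a rule on spacing. The 20 minutes stand between the sentence on adjusting the ventilator and the sentence on repeating the adjustment, so they may be the wait before the next clinical step. On that reading a 15-minute window sits safely before any further change, and the two sections do not collide. Part of this stands: the text says that the time is allowed, not that the effect is incomplete at 15 minutes. But the purpose it gives for the wait is the full effect, and a minute ending at 20 minutes is just as well protected from a repeat adjustment made after the wait.

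A reader might go further and infer that the 15-minute read-out makes reactivity wrong, and in particular too high because a skin sensor trails the blood. The documents do not support that. They give no delay for either signal and do not say which one lags. With no difference in delay, the ratio is unbiased however incomplete the response.

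It is also fair to say that the effects are modest. Section 3.6.2 sets no tolerance around 30%/kPa and no test, so a shift of about 1%/kPa is not shown to change a conclusion. How many episodes would be lost is unknown, because no distribution of tcpCO2 changes is given. Finally, a 20-minute read-out only reduces a delay bias; on the first-order assumptions roughly half of it remains.

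**Conclusion.** The inconsistency is certain; its consequences are modest and partly conditional. The analysis stops 5 minutes short of the protocol's own minimum for the full effect, without explanation, and so may use an incomplete response.

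- **If the response is still developing at 15 minutes**, the changes are smaller, the ratio is noisier, and slower episodes fail the 0.5 kPa rule. These effects need no difference in delay. With a first-order response 90-95% complete at 20 minutes, the changes are 91-94% of their 20-minute size, the error in the ratio is about 6-9% larger, and episodes between 0.50 and about 0.53-0.55 kPa are dropped. A straight ramp gives larger effects; a response 99% complete at 20 minutes gives almost none.
- **Bias in reactivity** is possible but not established. It needs different delays in CBFi and tcpCO2, would be larger at 15 than at 20 minutes, and could go either way.

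All of these sizes rest on assumed curves, not on figures in the protocol. The point is moderate: worth settling before data are seen, but not a flaw that invalidates this part of the study.

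**What to change.** Reconcile sections 3.4.3 and 3.6.2 on the analysis side only:

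- Set the post-change window to one fixed minute ending 20 minutes after the ventilator change, before any repeat adjustment.
- Apply the 0.5 kPa criterion over the same 20 minutes.
- Keep the 15-minute value as a sensitivity analysis.

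The window should be a fixed time. A window defined as the last minute before the next adjustment would vary between infants and depend on when clinicians act, which itself depends on the tcpCO2 being analysed. If the sponsor prefers 15 minutes as the primary read-out, section 3.6.2 should say why the response can be taken as sufficiently complete by then.

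The cost is a sentence or two in section 3.6.2. The recordings are already planned, and the clinical waiting time stays as it is. The protocol is a draft that is still to be turned into a clinical investigation plan, so the change fits that revision. The downside is that episodes without a clean 20-minute record drop out of the primary read-out; those with a clean record to 15 minutes can still enter the sensitivity analysis.
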